### **5.2.2. Packaging and Labeling**

Filgotinib and PTM filgotinib tablets are packaged in white, high density polyethylene (HDPE) bottles. Each bottle contains 30 tablets, silica gel desiccant and polyester packing material. Each bottle is enclosed with a white, continuous thread, child-resistant polypropylene screw cap fitted with an induction-sealed, aluminum-faced liner.

Study drugs to be distributed to centers in the US, EU and other participating countries shall be labeled to meet applicable requirements of the US Food and Drug Administration (FDA), EU Guideline to Good Manufacturing Practice – Annex 13 (Investigational Medicinal Products), and/or other local regulations, as applicable.

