### **5.3. Dosage and Administration**

The study medication will consist of 200 mg and 100 mg filgotinib tablets and PTM 200 mg and 100 mg filgotinib tablets for oral administration, to be taken once a day.

For missed dose(s) of study medication, subjects should be instructed to take the missed dose(s) of study medication as soon as possible during the same day. If the missed dose is not taken on the original day, then subjects should not take the missed dose and the missed dose should be returned to the study drug bottle. Subjects should be cautioned not to double the next dose (ie, taking the missed dose of study drug with that day's dose).

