### 6.3.3. Week 12 and Then Every 12 Weeks Thereafter From Day 1 ( $\pm 7$ days)

On Week 12 and then every 12 weeks thereafter from Day 1 until EoT or early discontinuation, the following evaluations are to be completed:

- Review AEs and concomitant medications
- Review e-Diary for completion and remind subjects of diary instructions
- Collect the variables to calculate CDAI score (reference [Appendix 4](#))
  - Site enters patient assessments at each visit
  - CDAI score calculated centrally after all components have been captured electronically
- PRO2 (reference [Appendix 4](#)) – calculated centrally
- Symptom-directed PE
- Complete perianal fistulae assessment (for subjects rolling over from GS-US-419-4016 **only**)
- Obtain weight
- Obtain vital signs (resting blood pressure, respiratory rate, pulse, and temperature)
- Obtain blood samples (reference Study Procedures Table [[Appendix 2](#)])
- Dispense study drug as directed by the IWRS

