4.2. Extent of Study Drug Exposure and Adherence

Extent of exposure to study drug will be examined by assessing the total duration of exposure to study drug and the level of adherence relative to the study drug regimen specified in the protocol.

If subjects are continuing study drug at the data cutoff date for an interim analysis, the data cutoff date will be used to impute the last dosing date for the calculation of duration of exposure to study drug and adherence to the study drug.

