4.2.2. Adherence to Study Drug

The total number of tablets taken will be summarized using descriptive statistics.

The presumed total number of tablets taken by a subject will be determined by the data collected on the drug accountability CRF using the following formula:

$$\text{Total Number of Tablets Taken} = \left(\sum \text{No. of Tablets Dispensed} \right) - \left(\sum \text{No. of Tablets Returned} \right)$$

If the bottle was not returned, it is assumed that the subject took all the study drug tablets from the dispensed bottle. The number of tablets returned will be imputed as zero for the given bottle for study drug adherence calculation purposes.

For calculation of the total number of tablets taken for the purposes of interim analyses (ie, prior to the return of all drug bottles), it will be assumed that each subject took the recommended daily dose from the dispensed bottle(s) until either the date of discontinuation, death or data cutoff date (whichever is earliest).

If the bottle has not been returned yet when the interim analysis is conducted, the number of tablets returned will be imputed as total pill count in the dispensed bottle – (the last dosing date – the last bottle dispensed date +1) for the given bottle for study drug adherence calculation purposes.

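### SAP 4.2.2's interim rule for unreturned bottles subtracts the same days from every bottle in a dispensing, so a three-bottle 12-week supply counts three times the tablets taken

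*SAP*

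**What the plan says.** SAP 4.2.2 defines tablets taken as the sum dispensed minus the sum returned, and 4.2.2.1 divides that by the amount expected during the on-treatment period. For interim analyses, 4.2.2 makes two further statements.

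- The general assumption: "it will be assumed that each subject took the recommended daily dose from the dispensed bottle(s", up to discontinuation, death or the data cutoff, whichever is earliest.
- The formula for a bottle not yet returned: "the number of tablets returned will be imputed as total pill count in the dispensed bottle" minus a count of days, namely the last dosing date minus "the last bottle dispensed date +1) for the given bottle for study drug adherence calculation purposes".

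For subjects still on drug at an interim, SAP 4.2 states that "the data cutoff date will be used to impute the last dosing date".

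The protocol supplies the rest. On packaging (5.2.2): "Each bottle contains 30 tablets, silica gel desiccant and polyester packing material". Tablets are "for oral administration, to be taken once a day" (5.3). From Week 12 on, the 12-weekly visit list in 6.3.3 includes "Dispense study drug as directed by the IWRS". The Study Procedures Table (Appendix 2) places dispensing at Day 1, Week 4, Week 12 and every 12 weeks after that. Neither document says how many bottles are given at a dispensing.

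**The concern.** The formula works bottle by bottle, but the days it subtracts belong to the whole dispensing. When several bottles of one tablet type go out on the same date, the same days are charged against each of them. There is no lower bound, so once more days have passed than a bottle holds tablets, the imputed return is negative and the subject is credited with tablets that were never dispensed.

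The stake is the interim adherence table. SAP 2.1 allows interim analyses for regulatory submission and/or publication, and SAP 4.2.2.1 gives an adherence category of 120% or more. A subject who took exactly one dose a day could appear there as over-dosing because of the algorithm alone. Real shortfalls in earlier supplies could be hidden by the same inflation.

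**Working it through.** The plan states no adherence figure to reproduce, so the check applies the rule as written and compares it with the daily-dose assumption in the same section.

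**Inputs.** 30 tablets per bottle (protocol 5.2.2); one tablet of each type per day (5.3); dispensing intervals of 28, 56 and then 84 days (Appendix 2). Assumption: the fewest bottles that cover the interval, that is 28/30, 56/30 and 84/30 rounded up to 1, 2 and 3 bottles per tablet type.

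**Formula.** Let e be the last dosing date minus the dispensing date plus 1, and n the number of unreturned bottles of one type.

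- Returned per bottle = 30 − e
- Taken = 30n − n(30 − e) = n·e
- Taken under the daily-dose assumption = e

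The overstatement factor is therefore n, whatever the value of e.

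| Supply | Bottles | e | Returned per bottle | Taken by the rule | Taken at one a day | Ratio |
|---|---|---|---|---|---|---|
| Day 1 to Week 4 | 1 | 28 | 2 | 28 | 28 | 1.0 |
| Week 4 to 12 | 2 | 28 | 2 | 56 | 28 | 2.0 |
| Week 4 to 12 | 2 | 56 | −26 | 112 | 56 | 2.0 |
| 12-week | 3 | 28 | 2 | 84 | 28 | 3.0 |
| 12-week | 3 | 61 | −31 | 183 | 61 | 3.0 |
| 12-week | 3 | 84 | −54 | 252 | 84 | 3.0 |

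Returns turn negative only when e exceeds 30, which is 54 of the 84 possible cutoff days in a 12-week supply (64%). The inflation is present at any e.

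**Blinded two-tablet regimen** (protocol Table 3-1), three bottles of each type: at e = 84 the rule gives 6 × 84 = 504 tablets against 2 × 84 = 168, again a ratio of 3.

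**Range on the bottle count.** A visit at the end of the +7-day window makes the interval 91 days; 91/30 rounds up to 4 bottles and the factor becomes 4. In general the factor equals the number of bottles of a type dispensed together, so an extra bottle at Day 1 would make even that supply wrong.

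**Overall adherence.** Only the current supply is inflated. If earlier supplies were fully taken and returned, then for T days on treatment within a three-bottle supply:

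adherence = (T − e + 3e)/T = (T + 2e)/T

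With e = 61, using the nominal visit days in SAP Table 3-1:

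- Dispensed at Week 12 (day 85), T = 145: (145 + 122)/145 = 184%
- Dispensed at Week 36 (day 253), T = 313: (313 + 122)/313 = 139%
- Dispensed at Week 84 (day 589), T = 649: (649 + 122)/649 = 119%

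The 120% line is crossed when 2e/T ≥ 0.20, so when T ≤ 10e: up to 420 days at e = 42, 610 days at e = 61, and 840 days at e = 84. For long exposure the effect shrinks. With 1260 earlier days and e = 42 it is (1260 + 126)/1302 = 106.5%; with 2436 earlier days and e = 42 it is (2436 + 126)/2478 = 103.4%.

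**The case against.** The strongest reply is that the intended result is already stated. The paragraph before the formula fixes one recommended dose per day, and the formula can be seen as loose single-bottle wording of it; for one bottle it is exact. A sensible programmer would not produce 300%. That is a fair account of the intent, but it does not repair the text. The formula refers to a single bottle at both ends, and the two statements cannot both be programmed for a multi-bottle supply. Other readings also fail:

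- Formula on the last bottle only, the others counted as fully taken: at e = 84, 60 + 84 = 144 tablets against 84 (1.71 times); at e = 28, 60 + 28 = 88 against 28 (3.14 times).
- All bottles pooled: right for one tablet type, but wrong for the blinded regimen. Six bottles give 180 − 84 = 96 returned, so 84 taken against 168 expected (50%).
- Pooling within tablet type works, but the SAP does not say so.

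The other limits stand. The bottle count is inferred. Interim analyses are permitted, the first is planned alongside the final analysis of GS-US-419-3895, and any of them may present only a subset of the planned analyses (SAP 2.1), so an interim adherence table is not certain. The adherence categories are given as examples.

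A reader might infer that every subject on drug at a cutoff is inflated, or that many will land at 120% or above. The documents support neither. On the minimum bottle count, the Day 1 to Week 4 supply is handled correctly, and nothing gives the distribution of time on study at a cutoff. A reader might also infer that the trial's safety results or final adherence figures are compromised; they are not, for the reasons under the verdict.

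**Conclusion.** The rule is wrong as written for any dispensing of more than one bottle per tablet type, and it contradicts the assumption stated just before it. On the minimum bottle count it is correct for the first four weeks, doubles the current supply's tablets taken from Week 4 to Week 12, and triples them in every later supply. Overall interim adherence for a fully adherent subject is (T + 2e)/T in a three-bottle supply: large early on, and a few percent after several years. How many subjects would cross 120% cannot be known from the documents.

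The reach is narrow. In the final analysis an unreturned bottle counts as zero returned, so the formula is not used. Exposure duration is computed from dates (SAP 4.2.1), the analysis sets do not depend on tablet counts (SAP 3.1), and adherence is not among the protocol's primary or secondary endpoints. The error should be corrected before any interim adherence or tablet-count table is issued, but it does not bear on the main conclusions.

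These figures rest on the minimum bottle count, one tablet of each type daily, and earlier supplies fully taken.

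**What to change.** Replace the last sentence of SAP 4.2.2 with a rule applied once per dispensing and tablet type:

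- Tablets taken from unreturned bottles = the lesser of (a) days covered by that dispensing × tablets of that type per day under the assigned regimen, and (b) total tablets in those bottles. Days covered run from the dispensing date to whichever comes first: the day before the next dispensing, the last dosing date, or the data cutoff.
- Tablets returned = the remainder, imputed once for the dispensing and bounded between zero and the tablets dispensed.

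Check: three bottles and 84 days give 90 − 84 = 6 returned and 84 taken, or 100%. With two tablet types, 6 of each are returned and 168 are taken against 168 expected.

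The cost is one SAP sentence and a small program change. If the SAP is not reopened, the change can be recorded in the clinical study report, as SAP Section 1 provides for changes after finalization. Any interim adherence output already produced should be checked against the program actually used, since the documents do not show how the rule was coded.

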4.2.2.1. On-Treatment Adherence

The level of on-treatment adherence to the study drug regimen will be determined by the total amount of study drug taken relative to the total amount of study drug expected to be taken during a subject's actual on-treatment period based on the study drug regimen.

The level of on-treatment adherence will be expressed as a percentage using the following formula:

$$\text{On - Treatment Adherence (\%)} = \left(\frac{\text{Total Amount of Study Drug Taken}}{\text{Study Drug Expected to be Taken on Treatment}} \right) \times 100$$

Descriptive statistics for the level of on-treatment adherence with the number and percentage of subjects belonging to adherence categories (eg, < 80%, ≥ 80 to < 90%, ≥ 90% to <120, ≥120) will be provided by treatment group for the Safety Analysis Set.

No formal statistical testing is planned.

A by-subject listing of study drug intake and drug accountability will be provided separately by subject ID number (in ascending order) and visit (in chronological order).

4.3. Protocol Deviations

Subjects who did not meet the eligibility criteria for study entry but enrolled in the study, will be summarized regardless of whether they were exempted by the sponsor or not. The summary will present the number and percentage of subjects who did not meet at least 1 eligibility criterion and the number of subjects who did not meet specific criteria by treatment group based on the All Enrolled Analysis Set. A by-subject listing will be provided for those subjects who did not meet at least 1 eligibility (inclusion or exclusion) criterion. The listing will present the eligibility criterion (or criteria if more than 1 deviation) that subjects did not meet and related comments, if collected.

Protocol deviations occurring after subjects entered the study are documented during routine monitoring. The number and percentage of subjects with important protocol deviations by

deviation category (eg, eligibility criteria, informed consent) will be summarized by treatment group for the All Enrolled Analysis Set. A by-subject listing will be provided for those subjects with important protocol deviations.

4.4. Assessment of COVID-19 (Coronavirus Disease 2019) and Ukrainian Conflict Impact

This study was ongoing during the COVID-19 pandemic and the conflict in Ukraine, which have an impact on study conduct. Some subjects were unable to attend onsite visits due to shelter-in-place guidelines, site closures, or other public health measures in response to these situations. This section describes how the impact on study conduct will be handled in the analysis.

4.4.1. Study Drug or Study Discontinuation

Summaries of reasons for discontinuing study drug or study due to COVID-19 will be provided by treatment group and overall, similar to the summary described in the subject enrollment and disposition section (see Section 4.1).

By-subject listing of reasons for premature study drug or study discontinuation due to COVID-19 will be provided if applicable.

4.4.2. Study Drug Interruption

Summaries of number of subjects with study drug interruption due to COVID-19 will be provided by treatment group, if applicable.

By-subject listings of study drug administration for subjects with study drug interruption due to COVID-19 will be provided, if applicable.

4.4.3. Protocol Deviations

Summaries of important protocol deviations due to COVID-19 will be provided, similar to the summary described in the protocol deviations section (Section 4.3).

By-subject listings will be provided for subjects with important protocol deviations related to COVID-19 and the Ukrainian conflict, if applicable.

4.4.4. Missed or Virtual Visits

Summaries of subjects with missed or virtual visits due to the COVID-19 pandemic will be provided for each scheduled study visit by treatment group and overall, for the All Enrolled Analysis Set. For each visit, the summaries will present the number and percentage of subjects who missed the visit due to COVID-19 or had a virtual visit due to COVID-19. For each column, the denominator for the percentage calculation will be the total number of subjects in the All Enrolled Analysis Set for that column.

Overall summaries of the number and percentage of subjects with missed or virtual visits (eg, subjects with at least 1 missed or virtual visit, subjects with 1, 2, 3 or more missed or virtual visits) due to COVID-19 will be provided by treatment group and overall, for the All Enrolled Analysis Set. The denominator for the percentage calculation will be the total number of subjects in the All Enrolled Analysis Set for that column.

By-subject listings of subjects with missed or virtual visits due to COVID-19 will be provided by subject ID number in ascending order.

Information regarding missed or virtual visits due to COVID-19 will be collected as free text in the CRF comment fields. The determination of missed or virtual visits due to COVID-19 will be done using Natural Language Processing (NLP) to search the CRF comment fields. A detailed explanation of the algorithm is given in [Appendix 3](#).

4.4.5. Adverse Events

By-subject listings will be provided for subjects with adverse events of COVID-19, as determined by COVID-19 Standardized MedDRA Query (SMQ) narrow search.

4.4.6. Comments

A by-subject listing of all comments related to the Ukrainian conflict will be provided.

5. BASELINE CHARACTERISTICS

5.1. Demographics and Baseline Characteristics

Subject demographic variables and baseline characteristics below will be summarized by treatment group and overall using descriptive statistics for continuous variables and using number and percentage of subjects for categorical variables. The summary of demographic data will be provided for the Safety Analysis Set. In addition, this summary will be provided for the induction non-responders (see Section 3.4), overall, and by prior exposure to biologic agents.

- Age (years, on the date of the first dose of study drug in Study GS-US-419-3896)
- Age group (< 65 years, ≥ 65 years)
- Sex at birth (female, male)
- Race
- Ethnicity (Hispanic or Latino, Not Hispanic or Latino)
- Geographic region (United States [US], non-US)
- Weight (in kg)
- Height (in cm)
- Body mass index (BMI; in kg/m²)

A by-subject demographic listing, including the informed consent date, will be provided by subject ID number in ascending order.

5.2. Other Baseline Characteristics

Other baseline characteristics include

- CDAI score
- PRO2 subscores: liquid or very soft stool subscore and abdominal pain subscore
- [REDACTED]
- [REDACTED]
- [REDACTED]
- Concomitant treatment at baseline

- Concomitant use of systemically absorbed corticosteroid and/or immunomodulator, including: a) systemically absorbed corticosteroid only, b) immunomodulator only, c) both, and d) neither
- Prednisone equivalence dose for subjects who are on systemically absorbed corticosteroid (mg/day)
- Prednisone equivalence dose level for subjects who are on systemically absorbed corticosteroid (> 0 to 10 mg/day, > 10 to 20 mg/day, > 20 to 30 mg/day, > 30 mg/day)
- 5-aminosalicylates (yes, no)

These baseline characteristics will be summarized by treatment group and overall using descriptive statistics for continuous variables and using number and percentage of subjects for categorical variables. The summary of these baseline characteristics will be provided for the Safety Analysis Set. In addition, this summary will be provided for the induction non-responders (see Section 3.4), overall, and by prior exposure to biologic agents.

No formal statistical testing is planned.

A by-subject listing of other baseline characteristics will be provided by subject ID number in ascending order.

5.3. Medical History

Adverse events which occurred in a parent study and were ongoing when subject took the first dose in this LTE study were recorded as medical history for Study GS-US-419-3896, excluding AEs occurred after Study GS-US-419-3896 informed consent is signed and prior to initiation of Day 1 Study GS-US-419-3896 IMP but related to Study GS-US-419-3896 protocol-mandated procedures.

General medical history data will be collected at enrollment and listed only. General medical history data will be coded using the current version of Medical Dictionary for Regulatory Activities (MedDRA).

6. EFFICACY ANALYSES

6.1. General Considerations

The efficacy analysis will be conducted on the Safety Analysis Set, defined in Section 3.1.2, unless otherwise specified.

6.1.1. Calculation of CDAI and PRO2 Scores

The CDAI system is a composite index of 8 disease activity variables with scores ranging from 0 to over 600 based upon a composite of symptoms (eg, abdominal pain), signs (the presence of abdominal mass and weight), laboratory values (eg, hematocrit), and physician assessment amongst others. The CDAI has 3 PRO components: liquid or very soft stool frequency, abdominal pain and general wellbeing. The total CDAI score is calculated as a weighted sum of all 8 component subscores. Clinical remission by CDAI is defined as CDAI score < 150 points. If subjects have 1 or more of the 8 component subscores missing, then the subjects will be considered as having insufficient data to determine remission status and their total CDAI score will be considered missing.

The PRO2 instrument has 2 components: liquid or very soft stool frequency subscore and abdominal pain subscore. Clinical remission by PRO2 is defined as an abdominal pain score ≤ 1 and liquid or very soft stool frequency ≤ 3 . If either subscore is missing, the subject will be considered as having insufficient data to determine clinical remission status by PRO2. For further information on the CDAI/PRO2 and calculation rules at baseline and postbaseline, reference is made to [Appendix 2](#).

6.2. Efficacy Endpoints

6.2.1. Definition of the Efficacy Endpoints

The secondary endpoints of this study are change in CDAI and PRO2 scores from baseline.

[REDACTED]

6.2.2. Analysis of the Efficacy Endpoints

CDAI and PRO2

Descriptive statistics and 95% CI based on normal approximation will be used to summarize the absolute values and change from baseline values in CDAI and PRO2 scores by analysis visit and treatment group using observed values. Mean absolute values of each score with 95% CI will be plotted over all analysis visits by treatment group. Mean change from baseline values of each score with 95% CI will also be plotted.

[REDACTED]

[REDACTED]

[REDACTED]

[REDACTED]

[REDACTED]

[REDACTED]

[REDACTED]

[REDACTED]

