1.2. Study Design

This is a long-term extension (LTE) study to evaluate the safety of filgotinib administered to subjects with CD. Some subjects will receive open-label drug and some will continue to receive the blinded study drug assigned in the parent study until subject's treatment in the corresponding parent study (GS-US-419-4015, GS-US-419-4016, or GS-US-419-3895) is unblinded. The duration of treatment is up to 432 weeks.

In general, subjects who fully complete a parent study blinded will continue blinded treatment at the same regimen in the present study on 200 mg filgotinib, 100 mg filgotinib, or placebo. Subjects who enroll from a parent study and receive blinded treatment in the GS-US-419-3896 study will have their GS-US-419-3896 treatment assignment unblinded when the parent study is unblinded. After the study unblinding, subjects will continue on the same dose of open-label filgotinib as they had been receiving in blinded treatment; whereas subjects on placebo treatment

will discontinue study drug and study participation. Subjects who exit a parent study due to disease worsening or failure to meet response or remission criteria will receive open-label 200 mg filgotinib, with the exception of US and Korea males in this category who were not considered biologic refractory who will receive open-label 100 mg filgotinib.

This study includes:

- Day 1
- Treatment Visits: Week 2, Week 4, Week 12, and then every 12 weeks thereafter
- Post-Treatment (PTx) safety assessments (30 days after the last dose of study drug) for subjects who complete all study treatment visits or discontinue early

For additional details, please see the Schedule of Assessments in [Appendix 1](#).

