1.3. Sample Size and Power

No formal hypothesis testing is planned for this study and sample size calculation is not conducted. All subjects who have completed or met protocol-specified efficacy discontinuation criteria in a parent study (GS-US-419-4015, GS-US-419-4016, or GS-US-419-3895) may enroll in this study. The projected number of subjects enrolled is approximately 1000.

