3.2. Subject Grouping

For analyses based on the Safety Analysis Set and [REDACTED], subjects will be grouped according to the actual treatment received. The actual treatment received will differ from the assigned treatment only when their actual treatment differs from assigned treatment for the entire treatment duration.

For analyses of baseline characteristics and efficacy endpoints in the subset of subjects who rolled over into the LTE due to failure to meet response/remission criteria at W10 (see Section 3.4 and Section 6.3), subjects will be grouped according to the actual treatment received in both the parent study and the LTE study.

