3.4. Subgroup Analyses

Subgroup analyses will be performed for the group of subjects who rolled over into the LTE due to failure to meet response/remission criteria at W10 (induction non-responders):

- Overall, and,
- By number of prior exposures to biologic agent (0 vs ≥ 1).

Subgroup analyses for efficacy endpoints are specified in Section 6.3.

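### SAP 6.2.2 bases the CDAI and PRO2 confidence intervals on a normal approximation at every visit, so they are too narrow at visits and in groups where few subjects remain (low severity)

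*SAP*

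**What the plan says.** SAP 6.2.2 states: "Descriptive statistics and 95% CI based on normal approximation will be used to summarize the absolute values and change from baseline values" of the CDAI and PRO2 scores, "by analysis visit and treatment group using observed values". It adds that "Mean absolute values of each score with 95% CI will be plotted over all analysis visits by treatment group", with a matching plot for the changes. The readable text gives no t-based alternative, no rule for small samples and no minimum n for showing an interval.

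On scale, SAP 1.3 says "The projected number of subjects enrolled is approximately 1000" and "No formal hypothesis testing is planned for this study and sample size calculation is not conducted". No number is given per treatment group or per visit. SAP 1.2 says "The duration of treatment is up to 432 weeks", and SAP Table 3-1 has analysis windows to Week 432. Protocol 3.4 puts maximum treatment at roughly 7.5 years and ends treatment earlier in a country where the drug reaches the market. Under Protocol 3.3, placebo subjects stop drug and leave the study once unblinded.

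**The concern.** A normal-quantile interval treats the SD as known. Here it is estimated from the subjects seen at that visit, so the multiplier should be the t quantile. The error always runs in one direction: the interval is too short.

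The design makes small cells likely somewhere. Follow-up is long, only observed values count, placebo subjects leave at unblinding, and one missing component out of eight makes the whole CDAI missing (SAP 6.1.1). With no testing planned, these intervals are the main statement of precision on the secondary endpoints. The plots would look most over-precise at the late visits, where a reader judges whether the effect lasts. SAP 2.1 allows interim outputs to be used for regulatory submission and publication.

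**Working it through.** The plan states no sample size per cell, SD or interval width, so there is no figure of its own to reproduce. The check has three parts.

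**1. Coverage and width.** With normal data and an estimated SD, mean ± 1.96·SD/√n covers the true mean with probability 2·F(1.96; n−1) − 1, where F is the t distribution function. The width ratio is t(0.975; n−1)/1.96. Neither depends on the SD.

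| n | t multiplier | Coverage of the 1.96 interval | t interval wider by |
|---|---|---|---|
| 5 | 2.776 | 87.8% | 42% |
| 10 | 2.262 | 91.8% | 15% |
| 20 | 2.093 | 93.5% | 7% |
| 30 | 2.045 | 94.0% | 4% |
| 50 | 2.010 | 94.4% | 2.5% |
| 100 | 1.984 | 94.7% | 1.2% |

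Coverage first reaches 94% at n=30 and 94.5% at n=57.

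**2. Are small cells plausible?** SAP Table 3-1 has 38 post-baseline windows: Weeks 2 and 4, plus 432/12 = 36 visits at 12-week spacing. The protocol maximum is 7.5 × 365.25 = 2739 days, or about 391 weeks. The Week 396 window opens on day 2732 and the Week 408 window on day 2816, so the last windows should hold few subjects or none.

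The documents give no retention rate or group size. As an assumption, let a group start with N subjects and keep a fraction r per year, so that n = N·r^(weeks/52.18).

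| Starting N (assumed) | Annual retention (assumed) | n at Week 288 | n at Week 384 |
|---|---|---|---|
| 100 | 80% | 29 | 19 |
| 100 | 70% | 14 | 7 |
| 100 | 60% | 6 | 2 |
| 600 | 80% | 175 | 116 |

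A small group can reach the range where the multiplier matters. A large group with good retention does not.

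**3. Does the t interval repair PRO2?** PRO2 subscores are rounded to integers (SAP Appendix 2). A simulation of 200,000 samples took a 0–3 pain score with assumed probabilities 0.45, 0.35, 0.15 and 0.05.

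| n | Coverage, 1.96 interval | Coverage, t interval |
|---|---|---|
| 5 | 85.9% | 89.6% |
| 10 | 91.1% | 92.2% |
| 20 | 93.2% | 94.1% |
| 30 | 93.5% | 94.6% |

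The t interval is better at each n, but in very small cells of a rounded score it does not restore 95%.

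**The case against.** The strongest reply is that nothing depends on these intervals. The study is descriptive, tests no hypothesis and adjusts for no multiplicity, and the readable text of Protocol 8.5 does not list confidence intervals at all. SAP Section 3 already requires n with either SD or SE for continuous summaries, so a reader of the tables can rebuild a t interval. The SAP never writes 1.96, and a programmer might produce t limits anyway. For durability, the larger limitation is that late means come only from subjects still in the study, which no choice of quantile addresses. All of this stands, and it is why severity is low. It does not remove the point: the plots carry no stated n, and a plan that names a normal approximation should not leave the multiplier to the programmer.

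A reader might also infer that the same intervals are used in small subgroup cells of induction non-responders. The documents do not support that as fact. The readable text of SAP 6.3 names no interval method and part of it is redacted, so silence there cannot be counted as an omission. Nor do those cells empty through ordinary dropout, because 6.3 carries the last score forward after discontinuation for any reason but study closure. If they are small, it is because of how they are split: SAP 3.2 says "subjects will be grouped according to the actual treatment received in both the parent study and the LTE study", and 3.4 divides further by prior biologic exposure. A full 3 × 2 × 2 cross would suggest 12 cells. Protocol Table 3-1 allows only five parent-to-extension combinations for non-responders from blinded treatment (200→200, 100→200, placebo→200, 100→100 and placebo→100 mg), hence at most 5 × 2 = 10.

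**Conclusion.** The point holds for the by-visit, by-group summaries and plots in SAP 6.2.2. Read literally, the stated method gives intervals that are too narrow in sparse cells. The shortfall is material below about n=30, and coverage falls to 87.8% at n=5. At n of 100 or more the difference is about 1% of width and can be ignored.

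The coverage figures assume normal data. How many cells are affected depends on group sizes and retention that the documents do not give; the attrition figures only illustrate. It would go too far to say that all 38 windows are affected, since early visits in large groups are not and the last windows may be empty. Low severity: no decision rests on these intervals.

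**What to change.** In SAP 6.2.2, specify that the 95% intervals are based on the t distribution with n−1 degrees of freedom, in place of the normal approximation, and print n under each visit in the plots. A minimum n for displaying an interval is optional; the argument for one is that t limits do not fully restore coverage for rounded PRO2 scores in very small cells. If the Section 6.3 subgroup tables take over the 6.2.2 method, make the same change there and say so.

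The cost is one phrase and a line of counts per plot. Intervals widen slightly at small n and hardly move at large n. The SAP is already final, and its Section 1 provides for recording later changes in the study report.
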